In a narrative review in Africa, Husain et al. found a wide range of prevalence of metabolic disorders in the HIV-positive population: diabetes 2.1% to 26.5%, pre-diabetes 20.2% to 43.5%, metabolic syndrome 13% to 58% and dyslipidaemia 13% to 70% 63. In Feleke, Fekade 64 cross-sectional study in Ethiopia, the prevalence of hyperlipidaemia was 56.9% in patients on ART for greater ≥ 1 year and among these, 38.2%, 54.2% and 17.8% had hypercholesterolemia, high LDL-c and hyperglycaemia, respectively. A study in a hospital setting in Cameroon showed that the prevalence of hypertension in patients on ART was twice that of ART-naïve patients (38% vs. 19%) 65. A longitudinal study in Senegal which had a median follow-up of 9 years for patients on ART found that 28% and 14% of them had hypertension and diabetes, respectively 66. In a study which assessed the burden of cardiometabolic risk factors among untreated HIV-positive Cameroonians, the prevalence of impaired fasting glucose, diabetes and metabolic syndrome was higher in ART-naïve than in healthy individuals (47% vs. 27%, 26% vs. 1%, and 47% vs. 21%, respectively) ⁶⁷. However, the prevalence of hypertension was high and comparable in both groups (41% vs. 44%). A longitudinal study in South African young women following them for 3 years after HIV infection showed that metabolic syndrome was 8.7% and 19.2% at HIV diagnosis and over 36 months, respectively ⁶⁸. These data suggest that on its own, HIV has an effect on the metabolic syndrome.

There are no published estimates of the prevalence of metabolic syndrome among adults living with HIV in Zambia. However, in a study where metabolic syndrome was evaluated among patients with type 2 diabetes, the burden was 73% using NCEP-ATP III criteria ⁶⁹, and higher in women as compared to men. A population-based survey found that the prevalence of hypertension, impaired glucose tolerance, and obesity were 34.8% (Goma et al., 2011), 4% ⁷⁰ and 14.2% ⁷¹, 19% ⁷² respectively. These findings may be different if focused on HIV-positive patients on ART. A cross-sectional survey at the Department of Medicine at University Teaching Hospital in 2017-2018 found that 19% of admissions involved cardiovascular disease; CVD was a leading cause of hospitalization in people with HIV and high CD4 counts during ART.

b. Risk factors for metabolic syndrome in HIV

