Evaluation activities will be conducted in 2 high-volume, ACHIEVE-supported facilities and their surrounding catchment areas, henceforth referred to as the "pilot study sites" in Lusaka Province. These sites will be selected from among the 4 sites undergoing in-depth formative assessment under Objective #1. Tentatively, the pilot sites will be Chilenje 1st level hospital and George urban health centre, subject to approval by our TAC and findings from our formative assessment. The "mini" stepped wedge pilot will include all HIV-infected adults aged 18 years and older seeking care at the two pilot sites. Inclusion in the nested cohort will require documented HIV infection, age ≥ 18 years and one or more cardio-metabolic conditions or risk factors of interest described below (i.e., hypertension, diabetes/ pre-diabetes, and/or dyslipidaemia).

d. Selection of participants, sampling methods, sample size, enrolment and follow-up procedures

TASKPEN Study v1.3 13 December 2021 Page | 26

i. Description and source of population and catchment area

Based on existing PLHIV volumes at high-volume ACHIEVE supported sites in Lusaka, we expect to survey at least ~188 PLHIV meeting patient survey eligibility criteria at each site at baseline, midline, and endline (i.e., ~564 at each site or ~1128 participants in total) and to recruit approximately 100 baseline survey participants into the nested cohort at each site (i.e., ~200 total). For outcome ascertainment in the surveys, we will check vital signs, anthropomorphic measurements, and biomarkers. For outcome ascertainment in the nested cohort, we will review SmartCare, LIMS, and other MOH and CIDRZ registers and augment the abstraction of these routine data with study-driven primary data collection. Study-driven primary data collection in the nested cohort will include administration of the adapted WHOQOL-HIV-BREF-Zam and discrete choice experiment (DCE) questionnaire to these ~200 participants.

For the implementation outcome evaluation, we will conduct: 1) In-Depth Interviews (IDIs) with patients; 2) Focus Group Discussions (FGDs) with NPHWs and community health workers participating in the delivery of the TASKPEN; and 3) Key Informant Interviews (KII) with key stakeholders, such as policy makers from the Ministry of Health (MOH) and Clinic In-Charges, critical to implementation of the TASKPEN intervention. A brief implementation survey will be conducted with FGD participants at the end of each FGD.

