ii. Participant inclusion criteria

For the cross-sectional patient surveys, we will include all adult males and females ≥18 years of age seeking routine HIV care at the two pilot sites during the pilot period.

For the nested cohort, the participant will need to be eligible and included in the patient survey done at baseline plus they will also need to have one or more of the following cardio-metabolic conditions or risk factors: 1) any current tobacco smoking; 2) hypertension as defined by WHO PEN (i.e., systolic blood pressure [SBP] ≥140 mmHg and/or diastolic blood pressure [DBP] ≥90 mmHg; 3) diabetes mellitus as defined by WHO PEN (i.e. random plasma glucose ≥ 11.1 mmol/L, fasting plasma glucose ≥ 7 mmol/L, and/or haemoglobin A1c ≥ 48 mmol/mol / ≥6.5%); 4) prediabetes (defined as having impaired fasting glucose of 6.1 to 6.9 mmol/L, impaired glucose tolerance with a two-hour, post-oral glucose tolerance test glucose ≥7.8 mmol/L but <11.1 mmol/L and a fasting plasma glucose <7.0 mmol/L, and/or haemoglobin A1c 42 to 48 mmol/mol or between 6.0–6.4%); and/or 5) dyslipidaemia (defined as total cholesterol >5.2 mmol/L or low density lipoprotein ≥3.4 mmol/L).

IDI participants must be emancipated HIV-infected adults ≥18 years of age who were enrolled in the nested cohort and had documented exposure to the TASKPEN intervention at a pilot site.

FGD / implementation survey participants must be: ≥18 years of age; a NPHW or community health worker (CHW)/ lay health provider involved with TASKPEN or integrated HIV/NCD service delivery; and generally familiar with HIV and/or NCD service delivery at their facility.

KII participants must be: ≥18 years of age; a facility-level ART or OPD clinic manager/ in-charge or policy maker at district, provincial, or national level in Zambia; and generally familiar with HIV and/or NCD-related issues in their community.

iii. Participant exclusion criteria

For the cross-sectional patient surveys, we will exclude adults who do not have documented evidence of HIV infection or who have not established HIV care at a study site. We will also exclude people unwilling or unable to provide written informed consent.

TASKPEN Study

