For the nested cohort component, we will exclude adults who have no documented evidence of HIV infection or a NCD of interest. We will also exclude people who did not participate in the baseline patient survey, are not likely to remain at the site for their care through the end of cohort follow-up, or unwilling/ unable to provide written informed consent.

We will exclude any potential IDI, FGD/ implementation survey, or KII participant if they are unwilling or unable to provide written informed consent.

iv. Justification of exclusion of any sub-segment of the population

We will not exclude any sub-segment of the adult population for the cross-sectional patient surveys. We have chosen to exclude infants, children, and adolescents under 18 years of age from this analysis as the mechanisms and systems built to support their care are unique, and because this population has a lower risk of cardio-metabolic complications of HIV.

v. Site sampling and randomization, including sample size and statistical power

The pilot sites for the formative evaluation will be selected based on their feasibility to deliver TASKPEN and to reflect different levels of the health system. For the mini stepped wedge study, the pilot sites will be Chilenje 1st level hospital and George urban health centre, subject to approval by our TAC and findings from our formative assessment. We will use a computer-generated allocation algorithm to randomize the time at which Chilenje and George will switch from standard of care to the TASKPEN intervention. This timing will be concealed from clusters and the trial team until ~4 weeks before the switch date.

Table 4. Study sites for the TASKPEN formative assessment.

Facility	Annual PLHIV (TX_CUI	% of TX_ clients with documented (within last 6 m	pressure measu	Avg. No. d	Health Level	Integration of NCD a care
Mtendere	6138	727 (11.84%)	719 (11.71%)	833	First	Partial integration (ART services available in outpatient department)
Chawama	10161	5599 (55.10%)	4485 (44.14%)	1353	Secondary	No integration
Chilenje	8083	7225 (89%)	6484 (80%)	1045	First	No integration
George	8785	1103 (13%)	38 (0.4)	1345	Primary	No integration

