For the nested cohort component, we will contact a consecutive sample of survey participants who we identify with a cardio-metabolic NCD through the survey and invite them to be followed in the cohort. For consenting participants, we will prospectively collect individual-level data, using existing routine data systems and study-specific case reporting forms, at the selected sites during the pilot period. Study staff will mention during baseline survey consent procedures that we may contact, by phone or in person, participants found to have a cardio-metabolic NCD via the survey and invite them to learn more

about the cohort at their next clinic visit. Phone recruitment for the nested cohort will be done using a recruitment script (Appendix D.i). For those interested, study staff working closely with facility staff will speak with potential cohort participants during their next clinic visit to sensitize them about the study and proceed with informed consent procedures if eligible and interested. The study procedures, risks, and benefits will be discussed in detail in Nyanja, Bemba, or English based on potential participant preference. The potential participant will have the opportunity to ask questions and deliberate before they decide whether or not they consent to participate.

For IDIs, potential participants identified to be eligible from among nested cohort participants will be contacted by phone or in person by study staff using study locator information. Study staff will ask if the potential participant might be interested in volunteering for the IDIs. IDI risks and benefits will be discussed in detail. The potential participant will have the opportunity to ask questions and deliberate before they decide whether or not they consent to the IDI. Where a potential participant declines to learn more about an IDI or to provide consent, we will identify a replacement from among other nested cohort participants until we achieve our IDI enrolment target.

For KIIs, participants identified to be eligible will be contacted by phone, email, or in-person by the MPIs or one of the co-investigators and will be given detailed information regarding the purpose of the KIIs, and will then be asked if they would be willing to participate. Because using a structured screening script may undermine the trust and personal rapport necessary to ensure key informant enrolment and honest responses to interview questions, a screening script will not be implemented for KIIs.

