At both sites, during a ~1-month "run in period," we will establish basic study infrastructure to enable quantitative data collection during the patient surveys. This will involve fully equipping study offices at the sites and ensuring information technology connectivity and available computer hardware. Then, study staff will begin data collection on cardio-metabolic and implementation outcomes of interest using three cross-sectional patient surveys. The first two surveys (at baseline [0 months] and midline [3 months] will be done immediately prior to a site switching to the intervention; a final survey will be done at 6 months and serve as the "endline" assessment. The surveys will ask questions about participant socio-demographics, HIV and cardio-metabolic NCD history, and health behaviours. It will involve trained study staff administering a tablet-based questionnaire to participants, as well as taking participants' anthropomorphic measurements (e.g., height, weight, and waste circumference), vital signs (e.g., pulse and blood pressure), and a small blood sample to measure random/ fasting blood glucose, haemoglobin A1c, cholesterol levels, and other biomarkers. These laboratory tests will follow MOH recommendations and may include new point-of-care diagnostic technologies (see laboratory procedures section), and the results will be reported to patients and the clinic for clinical management. Any participant found to have newly diagnosed hypertension, diabetes/ pre-diabetes, and/or dyslipidaemia will be linked to care at the study sites. In addition, the study QA/QC nurse and study clinical scientist/ doctor will be available to act immediately on any vital sign or laboratory abnormality, including to offer patient counselling, provide warm "handoffs" to clinical staff, refer patients for acute care at the study sites, and prescribe appropriate outpatient treatment for non-acute issues in cases where MOH staff are not available (e.g., after business hours). Finally, we will ask participants to provide a phone number so we can invite those identified with hypertension, diabetes/ pre-diabetes, and/or dyslipidaemia through the survey to be followed in the nested cohort.

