We will leverage the rich data from the nested cohort on cardiometabolic outcomes and covariates to make more accurate inferences about the distributions of these outcomes, and their trends over time, among all survey participants, as well as the target population of all PLHIV routinely in care at the study sites. Specifically, we will use outcomes measured in the nested cohort to account for measurement error (e.g., failure to capture a NCD diagnosis) or missing data (e.g., no record of a component of a given risk score) in the survey data and routinely collected medical record data. Rather than simply excluding records with missing data, considering those without a recorded diagnosis or biomarker value to be "outcome free," or using potentially mismeasured versions of the outcomes, we will address both measurement error and missing data using imputation approaches. These approaches fit models for the outcome of interest conditional on covariates among the nested cohort and use results to predict outcomes in the study population (i.e., survey participants) and the target population (i.e., all PLHIV in care at the study sites). We will report results from the nested cohort alone and after the imputation described above. To better understand the ability of the SmartCare EMR to capture routine NCD covariats and outcomes over time, we will also report the sensitivity and specificity of various measures obtained using the routine data only (assessed using data from the nested cohort as the gold standard) and the distribution of study-collected outcomes in the nested cohort among those with missing routine measurements.

DCE analysis: DCE questionnaire results will be analyzed by the mixed-effects logit model, which is commonly used to analyze DCE data and identify potential preference heterogeneity by the patients' key characteristics. The mixed-effects logit model calculates the relative mean preference weights per attribute. We will compare models with different random parameters using the Akaike information

criterion (AIC), Bayesian information criterion (BIC), and likelihood ratio tests for goodness-fit-test and select the final model.

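### Prediction models fitted only in a cohort selected for disease will over-project the baseline prevalence of threshold-defined conditions to all patients in care

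*Combined protocol and SAP*

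**What the plan says.** All sections below belong to Specific Objective #2 unless stated.

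**The models.** Section g.i uses the nested cohort to deal with measurement error and missing data in both the survey and the routine records. The models "fit models for the outcome of interest conditional on covariates among the nested cohort and use results to predict outcomes in the study population" (the survey participants) and in a target population of all people with HIV in care at the sites. The covariates are not named, and no weighting or other selection correction is given. Cohort-only results are also reported. The cohort is the reference standard for the sensitivity and specificity of routine SmartCare data.

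**Entry to the cohort.** Five places describe it:
- Section d.ii: "they will also need to have one or more of the following cardio-metabolic conditions or risk factors: 1) any current tobacco smoking", followed by hypertension, diabetes, prediabetes and dyslipidaemia, each defined by measured values.
- Section c: "one or more cardio-metabolic conditions or risk factors of interest described below (i.e., hypertension, diabetes/ pre-diabetes, and/or dyslipidaemia".
- Section d.iii: "we will exclude adults who have no documented evidence of HIV infection or a NCD of interest", along with people who "are not likely to remain at the site for their care through the end of cohort follow-up".
- Section d.vi: "we will contact a consecutive sample of survey participants who we identify with a cardio-metabolic NCD through the survey".
- Section e.iii: staff will "invite those identified with hypertension, diabetes/ pre-diabetes, and/or dyslipidaemia through the survey to be followed in the nested cohort".

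Smoking alone qualifies only in d.ii. Prediabetes qualifies in c, d.ii and e.iii. Sections d.iii and d.vi speak only of an NCD.

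**The survey.** Under section e.vi every survey participant is tested for glucose, haemoglobin A1c and lipids, and study results are also entered in the routine record. Section g.i first says that the effect is estimated from survey percentages and that missing values will not be imputed. It later describes imputation for the survey data.

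**The concern.** The models learn from people chosen because they have at least one of the outcomes being predicted, and are then applied to people who were not chosen that way. Conditioning on covariates does not undo selection on the outcome itself. A survey participant who met no criterion never enters the cohort, so the cohort also cannot show how often diagnoses were missed in such people.

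At stake are the projected NCD burden among all patients in care and the stated accuracy of SmartCare, both meant to inform the larger trial. The projections would lean heavily on the model, because section e.vi says that lipid and haemoglobin A1c tests are not usually available in routine practice.

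**Working it through.** **1. The plan's own figures.** Section b derives the cohort size as 188 × 0.50 = 94 per site, stated as about 100 (100/188 = 53%). Both are marked approximate, so they agree well enough. The 50% counts hypertension, diabetes and dyslipidaemia only. The 80% power in section d.v concerns the direct survey comparison and reproduces at 80.03% (Hussey-Hughes variance, 2 clusters, 3 periods, 188 per cluster-period, total variance 0.6 × 0.4, intra-cluster correlation 0.25). Nothing below changes it.

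**2. The selection identity.** Let C be a condition defined by a d.ii threshold, S = 1 mean eligible for the cohort, and X the covariates. Everyone with C is eligible, so P(C and S = 1 | X) = P(C | X), and

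P(C | X, S = 1) = P(C | X) / P(S = 1 | X).

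If enrolment among eligible people does not depend on C given X, this is what the cohort model estimates. It is never below P(C | X), and equals it only where X already guarantees eligibility (or P(C | X) = 0).

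**3. Eligible share E, uninformative covariates.** E = 1 − 0.50 × (1 − prediabetes) × (1 − smoking). The 0.50 is from section b. The prediabetes range is from the literature review, section 5.a ("pre-diabetes 20.2% to 43.5" per cent). Smoking at 0 to 12% and independence are assumptions.

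| Entry wording | Prediabetes | Smoking | E | Inflation 1/E | Any of the three NCDs, projected (0.50/E) |
|---|---|---|---|---|---|
| NCD only (d.iii, d.vi) | not counted | not counted | 0.500 | 2.00 | 100% |
| Adds prediabetes | 0.202 | 0 | 0.601 | 1.66 | 83% |
| Adds both | 0.202 | 0.12 | 0.649 | 1.54 | 77% |
| Adds prediabetes | 0.435 | 0 | 0.718 | 1.39 | 70% |
| Adds both | 0.435 | 0.12 | 0.751 | 1.33 | 67% |

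The true value in the last column is 50% by assumption. Clustering of prediabetes with the other conditions would lower E. The near-exclusive prediabetes and diabetes ranges in d.ii pull the other way.

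**4. Informative covariates.** In a simulation of 400,000 people with five entry criteria and two covariates, logistic models were fitted in the eligible and applied to everyone. Projected over true prevalence was:

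| Eligible share | Hypertension: uninformative | Moderate | Stronger | Diabetes: stronger |
|---|---|---|---|---|
| 50% | 2.00 | 1.91 | 1.71 | 1.39 |
| 60% | 1.67 | 1.60 | 1.45 | 1.24 |
| 70% | 1.43 | 1.38 | 1.28 | 1.14 |

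At 50% eligible with moderate covariates, true hypertension was 25.5% and the cohort-trained projection 48.7%. Fitting on everyone, or multiplying the cohort prediction by P(S = 1 | X), returned 25.5%. A second simulation (200,000 people, any NCD set at 50%, E from 0.75 to 0.60) gave hypertension ratios of 1.25 to 1.53 at an AUC of 0.76 and 1.10 to 1.22 at an AUC of 0.93. The bias tends to zero as prediction becomes perfect.

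**5. SmartCare accuracy.** Sensitivity is the chance of a record given C. Everyone with threshold-defined C is eligible, so under the same enrolment assumption the restriction does not distort it. Specificity needs people without C, and in the cohort these all qualified through another criterion. For any qualifying condition taken together, the cohort contains no non-cases at baseline, so specificity cannot be estimated.

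**6. Share of records depending on prediction (illustration only).** Reading the Table 4 counts as documented blood pressure, 8,785 − 38 = 8,747 clients at George and 8,083 − 6,484 = 1,599 at Chilenje have none: 10,346 of 16,868, or 61%. The column heading is not fully legible, the data predate the study and the sites are tentative, so nothing rests on this figure.

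**The case against.** The best defence is scope. This is a secondary projection in a pilot. The cohort is not meant for hypothesis testing, cohort-only results are reported alongside, and good covariates would shrink the bias. That is all true and lowers the severity, but it does not make the projection correct.

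Three limits also stand. The identity needs everyone with the condition to be eligible. A diagnosed patient under control on treatment need not meet a d.ii threshold, so the direction is not established for diagnosis-type outcomes. At follow-up, treatment and regression to the mean make it uncertain too. The enrolment assumption may not hold exactly, because d.iii also excludes people unlikely to stay at the site.

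A reader might infer more than the documents support:
- *That the intervention effect is biased.* Section g.i bases it on survey percentages without imputation. Bias by this route arises only if the later imputation text is allowed to override that rule. Whether cohort members' repeat surveys are pooled into the comparison is a separate question.
- *That dual control would be under-projected by a known amount.* The imputation text does not name dual control. The plan's inputs also conflict: if about 50% exceed an NCD threshold, dual control as defined under Outcomes could hardly reach the 60% assumed in d.v, unless many have diastolic-only hypertension or controlled disease. No figure is offered.
- *That SmartCare accuracy is biased throughout.* Sensitivity for threshold-defined conditions is not distorted, on the assumption above. Specificity is biased only if false-positive recording differs between cohort non-cases and other patients, which the documents do not show.

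**Conclusion.** The concern holds in a limited form. As written, section g.i would over-project the baseline prevalence of threshold-defined conditions to survey participants and to all patients in care. The factor is about 1.33 to 2.0 with uninformative covariates, and smaller with informative ones.

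The direction rests on two assumptions: the condition itself confers eligibility, and enrolment among eligible people does not depend on it given covariates. The size rests on the assumed eligible share of 75% to 50%, and so partly on which entry wording applies. The documents do not fix it.

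SmartCare specificity rests on a restricted group and cannot be estimated for any qualifying condition taken together. The direct survey comparison is untouched if the no-imputation rule governs it. The point should be fixed before analysis, but it does not undermine the pilot's main comparison.

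**What to change.** 1. Fit the prevalence, missing-data and projection models on all directly tested survey participants, with survey round and intervention period as covariates. At baseline this adds about 93 to 188 of 376 people who meet no entry criterion (376 × 0.249 to 376 × 0.50). Alternatively, for threshold-defined conditions, multiply cohort predictions by P(eligible | X) estimated from the full survey. Either way, state the assumption that consecutive attenders represent all patients in care given the covariates.
2. Estimate SmartCare sensitivity and specificity in that full sample, using only routine entries dated before the survey visit, because study results are written into the routine record.
3. Limit cohort-based corrections and trends to people who meet cohort eligibility, and say that missed diagnoses in others stay uncorrected.
4. Reconcile the two statements in g.i, for example: *The control-versus-intervention comparison uses no imputed values; imputation is a labelled secondary analysis.*

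Reconciling the cohort-entry wording across sections c, d.ii, d.iii, d.vi and e.iii is a separate minor point, though it determines the eligible share.

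**Cost.** No new measurements. There is extra analysis and possibly record linkage for survey participants outside the cohort: 1,128 − 200 = 928 people if all those surveyed are distinct, or 1,128 − 3 × 200 = 528 if cohort members count in all three rounds. The Outcomes and data-management sections (e.vii and f.ii) already partly imply such linkage. A consent or ethics check may still be needed, because e.iii specifies identifiers for cohort members, while d.v and section 9.h describe the wider routine-data review as de-identified.
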